3.6 Trial Visits

Screening Visit

A preliminary evaluation of eligibility for the trial should be made by the site investigator before informed consent is obtained. Once written informed consent is obtained the patient will be allocated a Participant Identification Number (PIN) and the screening and baseline assessments will be completed, including details of the infant's clinical status, grade of IVH and ventricular indices. The screening and baseline visits can occur on the same day as long as the infant's parent/guardian(s) have been given time to reflect on the information in the PIS and following a discussion with a medically qualified investigator where they have and been given the opportunity to ask questions.

Baseline Visit

Infant's parent/guardian(s) must give written informed consent before any trial specific investigations may be carried out. The following assessments or procedures are required within 7 days prior to randomisation and are required to confirm eligibility.

- Papile grade
- Cranial Ultrasound the ultrasound scan used to confirm eligibility will be stored by sites and a copy sent to Great Ormond Street Hospital where they will be uploaded and stored in the Data Safe Haven. Please see Imaging Transfer Guidelines for further details.
- Head circumference
- Birth weight
- Routine blood results for Haematology, Biochemistry & Coagulation/clotting
- Imaging history
- •
- Clinical Assessment
- Signs of Raised ICP

Questionnaires:

• EuroQoL EQ-5D-5L

The infant's parent/guardian(s) should complete the EuroQoL EQ-5D-5L Quality of Life questionnaire. This is required to be completed within 28 days prior to randomisation as it is not required to confirm eligibility.

Questionnaires should be completed at the start of the visit before any other procedures are performed. The completed questionnaire responses to the EQ-5D-5L must be reviewed during the visit to check for self-reported 'severe' or 'extreme' anxiety and depression. Parents/guardians reporting these symptoms should be signposted to access support from their healthcare provider e.g., their GP.

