In cases where the questionnaires have been returned to the research team by post, the EQ-5D-5L responses must be assessed by a member of the research team as soon as they are received to check for self-reported 'severe' or 'extreme' anxiety and depression. Parents/guardians reporting these symptoms should be contacted and signposted to access support from their healthcare provider e.g., their GP.

18 Months of Age Follow-Up (+/- 2 months) – (Telephone Follow-Up)

This visit should take place at 18 months of age (+/-2 months). The following assessments will be undertaken:

Review of Adverse Events

Questionnaires (Telephone Interview):

Adapted Client Service Receipt Inventory (CSRI children version)

2 Years corrected Age Follow-Up (+/- 2 months)

This visit should take place at 2 years corrected age (+/-2 months). The following assessments will be undertaken on two separate visits as follows:

The following assessments performed by a member of the research team at site:

- Weight
- Head circumference
- Incidence of seizures
- Wound site check
- Clinical Assessment
- Review of Shunt/Temporising Device information
- Review of Adverse Events
- Review of Concomitant medications for prophylactic antibiotics and anti-epileptic medications prescribed.

Questionnaires:

- EuroQoL EQ-5D-5L
- Adapted Client Service Receipt Inventory (CSRI children version)
- TNO-AZL TAPQOL
- Brief Infant Toddler Social Emotional Assessment (BITSEA)
- Quantitative Checklist for Autism in Toddlers (Q-CHAT)

Questionnaires should be completed at the start of the visit before any other procedures are performed. The completed questionnaire responses to the EQ-5D-5L must be reviewed during the visit to check for self-reported 'severe' or 'extreme' anxiety and depression. Parents/guardians reporting these symptoms should be signposted to access support from their healthcare provider e.g., their GP.

In cases where the questionnaires have been returned to the research team by post, the EQ-5D-5L responses must be assessed by a member of the research team as soon as they are received to check for self-reported 'severe' or 'extreme' anxiety and depression. Parents/guardians reporting these symptoms should be contacted and signposted to access support from their healthcare provider e.g., their GP.

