5.1.2 Secondary Outcomes

The secondary outcome measures are:

- 1. Developmental Measures:
 - a. Motor quotient (MQ): Age equivalent motor score of the Bayley IV divided by corrected age at assessment, measured at 2 years' corrected age
 - b. Language quotient (LQ): Age equivalent language score of the Bayley IV divided by corrected age at assessment, measured at 2 years' corrected age
- 2. Other neurological and functional assessments conducted during the 2-year follow-up visit:
 - a. Presence of seizures during the first 2 years and use of anticonvulsant medication at 2 years.
 - Presence of cerebral palsy (+ accompanying Gross Motor Function Classification System (GMFCS) grade and deficit distribution map using the Classification of SCPE
 - c. Assessment of hearing and vision (British Association of Perinatal Medicine classification)
 - d. Parent report:
 - i. Brief Infant Toddler Social Emotional Assessment (BITSEA)
 - ii. Quantitative Checklist for Autism in Toddlers (Q-CHAT)
- 3. Mortality up to 2 years corrected age.
- 4. NEL & VP shunt related outcomes:

- a. Safety of NEL: Number of Adverse Events, where Adverse Events would include (and not limited to) secondary bleeding in the brain, post-operative infections, temporising device survival, mortality, stroke, seizures, electrolyte disturbances, CSF leak, unexpected readmissions or return to theatre.
- b. Number and type of further surgical procedures, including revision of the temporising drainage device (VAD or VSG), addition of a second temporising device, surgery for loculated or isolated ventricles, and revisions of the VP shunt, if implanted, until two years' corrected age. These infants often need multiple shunt revisions during their first two years of life. We will have a separate CRF to record data related to these unexpected presentations and procedures.
- c. Requirement for permanent VP shunt insertion at 6 months' corrected age. (This is at the discretion of the treating team in the participating centre, according to routine clinical care).
- 5. Quality of life and health economic assessments:
 - a. Health-Related Quality of Life (HRQoL) in children: TNO-AZL Preschool Children's Quality of Life (TAPQOL) to be assessed at 12-months and 2 years' corrected age
 - b. HRQoL in primary caregiver: EuroQoL EQ-5D-5L to be assessed at baseline, 6 months, 12 months- and 2 years' corrected age

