5.2 Participant TimelineTable 1. ENLIVEN-UK Participant Schedule of Assessments

	Screening Visit ¹	Baseline Visit ³	Surgery (t=0)	Post- Operative Follow Up (t=24-48h)	First Clinical Follow Up (t=term equivalent	VP Shunt Insertion (if required)	3-6 Months Clinical Follow Up Visit	Age 1 Year Clinical Follow Up	18 Month Follow Up	2 Years corrected Age Clinical Follow Up	Unschedule d Visit to Neuro- surgical Unit ¹⁵
		Within 7 days prior to surgery (t=0)			+/- 1 month		+/- 2 months	+/- 2 months	+/- 2 months	+/- 2 months	
Informed consent	Х										
Eligibility ²	Х	х									
Papile grade		Х									
Birth Weight		х									
Cranial ultrasound ⁴		Х		Х		Х					
Haematology ⁵		Х		Х							
Biochemistry ⁶		Х		Х							
Coagulation/Clotting		х		х							
Imaging History ¹⁷		х									
Signs of raised ICP		х									
Randomisation			Х								
Physical Examination ⁸											х
Study Procedure (NEL+TD / TD alone) ¹¹			Х								

39

	Screening Visit ¹	Baseline Visit ³	Surgery (t=0)	Post- Operative Follow Up (t=24-48h)	First Clinical Follow Up (t=term equivalent	VP Shunt Insertion (if required)	3-6 Months Clinical Follow Up Visit	Age 1 Year Clinical Follow Up	18 Month Follow Up	2 Years corrected Age Clinical Follow Up	Unschedule d Visit to Neuro- surgical Unit ¹⁵
		Within 7 days prior to surgery (t=0)			+/- 1 month		+/- 2 months	+/- 2 months	+/- 2 months	+/- 2 months	
Discharge Information				х							
Head Circumference		х		Х	х	Х	х	х		Х	Х
Incidence of Seizures										Х	
Wound Site Check				Х	Х					Х	Х
CSF sample collection (optional) ¹⁶			Х			х					Х
Research Blood sample collection (optional) ¹⁶			Х			х					Х
Clinical Assessment ¹²		х		Х	Х	Х	Х	Х		Х	Х
Shunt/Temporising Device Information				х	Х	х	Х	Х		х	х
Adverse events Review			Х	X	Х	х	Х	Х	Х	х	Х
Concomitant Medication Review ¹³			Х	х	Х					х	
MRI (as per Standard of Care) ⁴					Х						Х
EuroQoL EQ-5D-5L ¹⁹		Х					X ¹⁸	Х		Х	
Adapted CSRI (children version)							Х	Х	Х	х	
TNO-AZL TAPQOL								Х		Х	
Bayley IV Scales ⁹										Х	

	Screening Visit ¹	Baseline Visit ³	Surgery (t=0)	Post- Operative Follow Up (t=24-48h)	First Clinical Follow Up (t=term equivalent	VP Shunt Insertion (if required)	3-6 Months Clinical Follow Up Visit	Age 1 Year Clinical Follow Up	18 Month Follow Up	2 Years corrected Age Clinical Follow Up	Unschedule d Visit to Neuro- surgical Unit ¹⁵
		Within 7 days prior to surgery (t=0)			+/- 1 month		+/- 2 months	+/- 2 months	+/- 2 months	+/- 2 months	
Cerebral palsy assessment 9, 10										Х	

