Vision and hearing assessment (BAPM classification) ⁹										х	
Brief Infant Toddler Social Emotional Assessment (BITSEA)										х	
Quantitative Checklist for Autism in Toddlers (Q-CHAT)										х	

¹ Screening and baseline visit can occur on the same day if the infant's parent/guardian(s) have been given time to reflect on the information in the PIS and following a discussion with a medically qualified investigator where they have and been given the opportunity to ask questions.

Standard of care MRI scans may be submitted for review and storage for all infants where available and if performed as standard of care assessment only.

Please see Imaging Transfer Guidelines for further details.

² Review inclusion and exclusion criteria and ensure eligibility prior to enrolment and randomisation.

³ Baseline Visit assessments to confirm eligibility for trial should be performed within 7 days of Surgery (t=0). Baseline EuroQoL EQ-5D-5L Quality of Life questionnaire can be completed within 28 days prior to randomisation as it is not required to confirm eligibility.

⁴ Investigators are required to submit images of Ultrasound scans for review and storage for all infants.

⁵ Haematology – including Haemoglobin, White Blood Cell Count, platelets as per routine standard of care

⁶ Biochemistry – including Sodium, Potassium, as per routine standard of care

- ⁷ Coagulation: including INR or APTT as per routine standard of care
- ⁸ Physical Examination: Including heart rate, temperature, Glasgow Coma Score. Results of routine **Blood tests for Neutrophils Erythrocyte Sedimentation Rate and C-Reactive Protein should be collected if performed as part of routine care.**
- ⁹ Assessments will be performed by a qualified and validated independent clinical development specialist blinded to the treatment arm.
- ¹⁰ CP subtype (SCPE) & Gross Motor Function Classification System (GMFCS) grade will be assessed
- ¹¹ For Arm A (Intervention) patients, details of the NEL procedure will be recorded in addition to Temporising device information
- ¹² Clinical assessment including weight, review of parental concerns
- ¹³ Review of Concomitant medications for prophylactic antibiotics and anti-epileptic medications prescribed.
- ¹⁴ See section 5.2.1 for details about the performing the 2-year clinical follow-up visit

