6.4.1.4 Expectedness

If there is at least a possible involvement of the trial intervention (NEL), the sponsor will assess the expectedness of the event. If information of expectedness is provided by the investigator this should be taken into consideration by the sponsor. An unexpected adverse event is one not reported in Table 6 NEL Risks and mitigations (**Section 6.3.1.5**).

6..1.5 Risks associated with NEL

The risks associated with NEL for the ENLIVEN-UK trial are listed in Table 6 (NEL risks and mitigations) below:

Table 6. NEL risks and mitigations.

POTENTIAL RISK	RISK MANAGEMENT
Infection	Procedure in strict sterile conditions in operating theatre as per standard practice. Peri-operative antibiotics are given and the choice of agent and duration will vary according to local guidelines.
Secondary bleeding	There is a clear consensus on surgical protocol to ensure maximal safe washout without causing secondary bleeding in the ventricles or in the brain. The surgeon should stop when they feel they have achieved a 'maximal safe washout' as defined in the consensus guideline (28).
Stroke	Procedure-related brain injury risk has not been reported with NEL and therefore, the

	risk is low. It will be identified if it occurs on
	the post-operative ultrasound scan.
CSF leak	Standard closure techniques will be used to
	protect against CSF leak and, if it develops,
	will be managed at the discretion of the
	treating surgeon.
Seizures	Seizures (up to CTCAE Grade 3) can arise
	as a result of the initial IVH or procedure-
	related brain injury. These have been
	reported with NEL but the risk is low. If it
	occurs, it will be managed at the discretion of
	the treating medical team including
	neurosurgeon and neonatologist.
Temporising device dysfunction	The TD may stop working adequately due to
	either blockage, insufficient drainage or
	infection. At this stage, the clinical team will
	make an assessment as to whether it needs
	to be revised or whether a permanent
	ventriculoperitoneal shunt needs to be
	placed. This management will remain at the
Flootrolyte/Codings imbalance	discretion of the treating neurosurgical team.
Electrolyte/Sodium imbalance	The use of irrigating solution may lead to
	disturbances in the serum level of sodium
	and other electrolytes. This will be mitigated
	by using appropriate irrigating solutions, such
	as Ringer Lactate or artificial CSF and by
	monitoring electrolyte levels in the serum as

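### The seizure-presence outcome (2a) has no post-randomisation start, so, read as age, it counts seizures that precede allocation and blunts the between-arm comparison

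*Protocol*

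**What the plan says.** Section 5.1.2 lists outcome 2a as "Presence of seizures during the first 2 years and use of anticonvulsant medication at 2 years". It has two parts: whether seizures were ever present over a period, and medication use at one point in time. The first part has an approximate end and no stated start.

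Item 4b of the same section describes its period by age: "These infants often need multiple shunt revisions during their first two years of life".

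The seizure item is scheduled once. Section 3.6 lists "Incidence of seizures" at the 2 years' corrected age visit, and the row "Incidence of Seizures" in Table 1 is marked only in that column.

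At baseline no seizure history is named. Section 3.6 asks for "details of the infant's clinical status, grade of IVH and ventricular indices", and a footnote to Table 1 describes the "Clinical assessment including weight, review of parental concerns". Anti-epileptic medication is first reviewed at the surgery visit.

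Table 6 (NEL risks and mitigations) says that seizures may occur "as a result of the initial IVH or procedure"-related brain injury. Under sections 3.1 and 4.1, an infant enters only after reaching the ventricular threshold despite two attempted punctures, and is randomised once in theatre.

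**The concern.** NEL cannot influence a seizure that happened before it. If such seizures make an infant outcome-positive, those infants carry no information about treatment, and the two arms look more alike than they are after randomisation.

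This matters in both directions. Section 1.4 says that the seizure risk with lavage is in theory slightly higher than with the device alone, so dilution could hide a small harm as easily as a benefit. Outcome 2a is also the only listed two-arm seizure comparison not limited by severity or seriousness. Under section 6.1.1 only serious or notifiable adverse events are recorded, and the seizure item in section 6.2 is confined to grade 3 and above within 48 hours of NEL.

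**Working it through.** **1. The plan's own figure.** The only power statement is for the primary outcome (section 8.1): 45 per arm, two-sided 5% Wilcoxon test, Beta(1,1) against Beta(10, 4.25), 90% power. Simulation gives 91.1% (20,000 replicates, asymptotic test) and 91.0% (4,000 replicates, exact test). Recruitment is 90/(1 − 0.10) = 100. The figure reproduces and does not depend on outcome 2a. The protocol states no rate, effect or power for seizures.

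**2. Does the window reach back before randomisation?** The wording fixes neither birth nor randomisation as the start. Item 4b, two entries later, uses age, and the visit at which 2a is collected is set by corrected age. On that reading, the interval from birth through haemorrhage, dilatation and two punctures lies inside the window and before allocation. Nothing in 2a excludes it.

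**3. Effect on the comparison.** Let q be the share of infants with a seizure before randomisation, equal in the two arms in expectation. Let s_C and s_T be the later seizure risks among infants without an earlier one.

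- Risk of ever having a seizure = q + (1 − q)·s
- Risk difference = (1 − q)·(s_C − s_T)

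If the window starts at randomisation, the risk difference is (1 − q)·d0 + q·d1. Here d0 and d1 are the treatment differences in infants without and with earlier seizures. The age-based window discards the term q·d1. If earlier and later seizures are independent, d0 = d1 and the risk difference shrinks by exactly (1 − q).

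**4. Illustration.** All rates here are assumed: s_C = 30%, s_T = 15%. Power at n = 45 per arm is Φ{[d − 1.96·√(2p̄(1 − p̄)/n)] / √([p1(1 − p1) + p2(1 − p2)]/n)}. For q = 0 this is Φ[(0.15 − 1.96 × 0.0880)/0.0866] = Φ(−0.26) = 40%.

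| q | Control | NEL | Risk difference (points) | Risk ratio | Power |
|---|---|---|---|---|---|
| 0 | 30.0% | 15.0% | 15.0 | 0.50 | 40% |
| 10% | 37.0% | 23.5% | 13.5 | 0.64 | 28% |
| 20% | 44.0% | 32.0% | 12.0 | 0.73 | 21% |
| 30% | 51.0% | 40.5% | 10.5 | 0.79 | 17% |
| 40% | 58.0% | 49.0% | 9.0 | 0.84 | 13% |
| 50% | 65.0% | 57.5% | 7.5 | 0.88 | 11% |

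With 40% against 20% assumed, power is 55% at q = 0, 33% at q = 20% and 17% at q = 50%. With 20% against 10% it is 26%, 12.5% and 7%.

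**The case against.** The best defence is that the text never says from birth. A reader might infer an explicit rule that counts from birth, but the documents support only an undefined start whose natural reading is age. Mortality (item 3) has no stated start either, and no one would misapply it. Section 8.3.1 also leaves further detail to a standalone SAP. The first part of this stands as a limit on the claim. The mortality parallel does not help, because a death cannot precede enrolment and a seizure can. Nor can an SAP analyse a baseline variable that the protocol's schedule does not collect.

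A reader might also infer that earlier seizures can never be separated out. That goes too far. Clinical status is recorded at screening and baseline. Section 6.1.1 refers to episodic events first recorded there, section 6.2 speaks of newly developed seizures, and anti-epileptic drugs are reviewed at surgery. Neonatal notes exist as well. None of these is a named seizure-history item, however. The drug review misses untreated seizures, and section 3.5 shows that some infants arrive from other hospitals.

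A third inference is that seizure safety is compromised throughout. It is not. Outcome 4a covers seizures as adverse events, serious and notifiable events are collected from randomisation (section 6.4.2.1), and seizures more than 48 hours from the procedure are a listed foreseeable SAE (section 6.1.2.1). Anticonvulsant use at 2 years is a point-in-time measure and does not accumulate early seizures.

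Finally, the trial is powered on CQ alone. Even at q = 0 the illustrated seizure comparison has only 40% power, so it was never going to be decisive.

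**Conclusion.** The point holds for the seizure-presence part of outcome 2a. Its window has no post-randomisation start. On the natural reading it admits seizures that NEL cannot affect, and no named baseline item separates them.

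The cost is attenuation: a factor of (1 − q) on the risk difference, with the risk ratio moved towards 1. That factor assumes equal q in both arms and independence of earlier and later seizures. If NEL has no effect in infants with earlier seizures, d1 = 0, the risk difference is the same under either window, and the loss lies elsewhere, chiefly in precision. The size cannot be set from the protocol, because q is not given and every rate in the table is assumed.

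It would be wrong to read this as a source of false-positive results. Randomisation balances earlier seizures in expectation. A chance imbalance is possible at about 50 per arm, but that is true of any baseline characteristic. The primary outcome is untouched. This is a worthwhile correction to one secondary outcome.

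**What to change.** - **Outcome 2a:** define the seizure part as any seizure from randomisation to 2 years' corrected age. Starting at randomisation rather than at the end of the procedure keeps intra-operative seizures. Naming corrected age aligns the end of the window with the visit at which the item is collected.
- **2-year visit:** word the seizure-incidence item to ask about the same period.
- **Baseline:** add one field taken from existing notes, recording seizures before randomisation (yes/no, with date of the last). Use it as an adjustment variable, or to report the outcome also in infants seizure-free at baseline.
- **Infants already enrolled:** back-fill the field from their records.

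The cost is one extra CRF field, a one-line change to the outcome definition and a minor amendment. Visits, treatment and sample size do not change.

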The intervention being evaluated in this randomised trial, NEL will be carried out in addition to insertion of a temporising device (Arm A - Intervention). In our experience and in published studies, the additional risks of endoscopic lavage are low, and occur in less than 5% of cases

(21-25). The risks relate to standard neuro-endoscopic surgery and are expected to be lower than the risks of DRIFT. These include infection, further haemorrhage within the ventricles, haemorrhage related to ventricular decompression, seizures, CSF leak, electrolyte disturbance and a <1% risk of brain injury (21-25). These risks are not expected to be significantly higher than insertion of a temporising device alone. In theory the risk of electrolyte disturbance and seizures, related to the presence of lavage fluid within the ventricles, is slightly higher than with insertion of a temporizing device. This will be mitigated by use of warm Ringer lactate solution or artificial CSF, and by monitoring of serum electrolytes post-lavage. These infants are routinely cared for within a neonatal intensive care unit environment and close care and supervision is routine.

Several published studies have suggested that the requirement for permanent CSF diversion through a ventricular peritoneal shunt is reduced after lavage compared to insertion of a temporising device alone (22,24,25). This is a potential additional advantage of NEL that will be evaluated as an exploratory outcome.

The risks associated with NEL will be mitigated by ensuring that patient recruitment will only take place in established paediatric neurosurgical units and will be undertaken by paediatric neurosurgeons who routinely perform a range of neuro-endoscopic procedures. Each paediatric neurosurgical unit is affiliated with a neonatal unit to ensure appropriate neonatal care. A number of meetings have taken place to discuss the technical details of the irrigation procedure, and a surgical consensus statement has been published (28). In addition, a meeting with world experts in endoscopic lavage in this population is planned before commencement of recruitment to enable a wider discussion and sharing of operative nuances, experience and knowledge.

2 Selection of Sites/Investigators

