6.1.2 Serious Adverse Events

6.1.2.1 Foreseeable (expected) SAEs

The following are 'Foreseeable SAEs' that could be reasonably anticipated to occur in this population of infants during the course of the trial or form part of the outcome data.

They do not require expedited reporting by trial centres as SAEs **unless considered causally related** to the intervention (NEL) in which case they should be reported within 24 hours of site staff becoming aware of them as detailed in section 6.3.2.

'Foreseeable SAEs' that are **casually related** to the trial intervention (NEL) should be reported within 24 hours of site staff becoming aware of them using the SAE report form.

Foreseeable SAEs that are **not considered causally related** to the trial intervention (NEL) should be reported within 5 working days. Therefore, all Foreseeable SAEs occurring for patients in Arm B (Temporising device alone) will be not related to NEL and should be reported within 5 days.

Foreseeable SAEs:

- Necrotising enterocolitis or gastrointestinal perforation
- Intracranial abnormality (intraventricular haemorrhage or white matter damage) on cranial ultrasound scan or other imaging
- Seizures outside of 48 hours the procedure
- Pulmonary hypertension
- Hydrocephalus
- Respiratory distress syndrome
- Bronchopulmonary dysplasia or chronic lung disease
- Retinopathy of prematurity
- Early or late-onset Sepsis
- Patent ductus arteriosus (PDA)
- Pulmonary haemorrhage
- Pneumothorax
- Anaemia
- Hyperbilirubinaemia/jaundice
- Hypoglycaemia
- Hyperglycaemia
- Coagulopathy
- Liver cholestasis
- Liver failure
- Hypotension
- Hypertension
- Impaired renal function
- Extravasation injury
- Fractures
- Return to hospital for suspected or actual shunt malfunction or other neonatal condition unrelated to hydrocephalus after discharge from the neonatal unit, (unless readmission following initial discharge from hospital for grade 3 and above events)

6.1.2.2 'Unforeseeable SAEs' – (All SAEs not listed as 'Foreseeable SAEs')

All other SAEs occurring in trial participants which are not listed as Foreseeable SAEs in Section 6.1.2.1 are classed as unforeseeable SAEs and must be reported immediately after site staff become aware of the event (in no circumstances should this notification take longer than 24 hours) (see section 6.3).

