8.2.3 Allocation concealment mechanism and Blinding

This is a trial in which the primary outcome assessor, the Trial Statistician and the Clinical Project Manager will be blinded to the treatment allocation. The treating neurosurgeon and associated team cannot be blinded to treatment allocation due to nature of the study. Parents/legal guardians will be informed of the allocation after the procedure is completed. Parents will be informed by study team prior to the assessment that the assessor will be blinded to the treatment allocation, and they should therefore not divulge this information to the assessor inadvertently, which will be reinforced by the assessor before evaluation commences. All users of the Sealed Envelope system, with the exception of the Trial Statistician and the Clinical Project Manager, will be unblinded to treatment allocation via email and with the treatment allocated accessible through a secure portal, prior to the procedure being performed.

Given the study design, the treating neurosurgeon and associated research team cannot be blinded to treatment allocation. The increased operating time will also result in the Neonatal Intensive Care Unit (NICU) team being aware of the treatment arm. Previous Patient Advisory Group (PAG) work has identified that parents would like to be informed of the allocation and, failing to do so may result in many parents not taking part.

However, the primary outcome measure and other components of the Bayley IV developmental outcomes at 2 years' corrected age will be carried out by assessors blind to the treatment allocation.

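### Outcome 2a covers seizures over the first two years, but its only dedicated item is at the 2-year visit and no other record is stated to feed it

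*Protocol*

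**What the plan says.** Protocol 5.1.2 lists, under "Other neurological and functional assessments conducted during the 2-year follow-up visit", outcome 2a: "Presence of seizures during the first 2 years and use of anticonvulsant medication at 2 years". In Table 1 (5.2) the row "Incidence of Seizures" has one mark, in the 2-year corrected-age column. Section 3.6 agrees, placing the item in the list headed "The following assessments performed by a member of the research team at site". Table 2 (5.2.1) gives cerebral palsy, vision and hearing to the independent blinded assessor, but seizures to the neurosurgical follow-up. Section 8.2.3 says the neurosurgeon and associated research team cannot be blinded.

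Seizures also appear elsewhere:
- Safety outcome 4a (5.1.2) names them among the adverse events to be counted.
- Section 6.2 makes a new seizure of grade 3 or above within 48 hours of NEL a notifiable event.
- Section 6.1.2.1 lists "Seizures outside of 48 hours the procedure" among the foreseeable SAEs.
- Section 6.4.2.1 runs SAE and notifiable-event reporting from randomisation to the 2-year visit.
- Section 6.1.1 limits the adverse events recorded for the trial to those that are serious or notifiable.

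On risk, section 1.4 says: "In theory the risk of electrolyte disturbance and seizures, related to the presence of lavage fluid within the ventricles, is slightly higher than with" device insertion. It also says of the NEL risks as a group: "These risks are not expected to be significantly higher than insertion of a temporising device alone".

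**The concern.** An outcome defined over two years needs either collection throughout the two years or a rule for assembling it from records made along the way. The protocol gives 2a neither. Its item is scheduled once, at the end, and no text connects it to the adverse event or medication data gathered earlier.

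Three things follow. Milder seizures have no trial record until up to two years later. Infants without a 2-year visit are missing for 2a even when they attended every earlier contact. The early notifiable item is worded around a procedure that only one arm receives. Seizures are a listed outcome, a named component of 4a and a listed NEL risk in Table 6, so incomplete or uneven capture weakens a comparison the trial means to report. An analysis plan can define how existing records are combined, but it cannot recover events that were never entered.

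**Working it through.** No formula in the plan bears on this. The check sets the schedule, the safety rules and the retention allowance side by side.

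**Step 1: scheduled contacts (Table 1).**
- Dedicated seizure item: 1 column (2 years).
- Adverse event review: 9 columns (surgery, 24-48 h, term equivalent, VP shunt insertion, 3-6 months, 1 year, 18 months, 2 years, unscheduled).
- Medication review, which covers anti-epileptics: 4 columns (surgery, 24-48 h, term equivalent, 2 years).

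So 9 − 4 = 5 contact types have adverse event review but no anti-epileptic review: VP shunt insertion, 3-6 months, 1 year, 18 months and unscheduled.

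**Step 2: what the adverse event rules let through before 2 years (6.1 to 6.2).**

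| Seizure | Route into the database as an event |
|---|---|
| Any time, judged serious, either arm | SAE report |
| New, within 48 h, grade 3+, not judged serious, NEL arm | Notifiable event |
| New, within 48 h, grade 3+, not judged serious, control arm | None if 6.2 is read literally |
| Within 48 h, below grade 3, not judged serious | None until the 2-year item |
| After 48 h, not judged serious | None until the 2-year item |

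The third row arises because 6.2 times this item from NEL, whereas the matching foreseeable-SAE entry, "Seizures outside of 48 hours the procedure", refers only to the procedure, which both arms have. The medication review may leave an indirect trace of a seizure in any row, but a prescription is not a seizure record, and nothing says it counts towards 2a.

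**Step 3: infants without a 2-year visit.** Section 8.1 needs 90 infants and recruits 100, to allow 10% for loss to follow-up and other methodological challenges. That is 0.10 × 100 = 10, which equals 100 − 90. It does not say whether deaths fall inside the 10%. If they do, about 10 of 100 infants would have no 2a assessment. If deaths are additional, the number is larger by the number of deaths. The protocol gives no expected mortality, so no figure is put on that.

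**The case against.** The strongest reply is that seizures are collected throughout, and much of it stands. Serious and notifiable seizures are reported from randomisation to 2 years, and adverse event review takes place at every contact from surgery onward. Section 6.1 gives seizures without hospitalisation as an example of an event to be considered serious, so many later seizures should become SAEs. Early in follow-up, where a lavage effect would be expected, anti-epileptics are reviewed three times. Section 6.4 requires non-serious events to be written in the medical notes, so a 2-year entry could be drawn from those notes.

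A reader might go further than the text allows in four ways:
- **Seizures are collected only once.** That is true of the 2a item, not of seizure data.
- **The item is unblinded parental recall.** Section 8.2.3 does say "Parents/legal guardians will be informed of the allocation after the procedure is completed". But a site team member completes the item, section 7.4 says the CRF is not the source document for any data element, and outcome group 2 has a separate parent-report entry that does not include seizures.
- **Infants who die or leave early contribute nothing.** Section 5.5 keeps data already collected, and the section on treatment discontinuation includes them in analyses where possible. Their safety reports count in 4a. Only 2a is missing.
- **The protocol expects more seizures with NEL.** Section 1.4 says only that the risk is slightly higher in theory, and also "These risks are not expected to be significantly higher than insertion of a temporising device alone".

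It may also be said that deriving 2a belongs in the SAP. That holds for combining records and counting early leavers. It does not hold for seizures that 6.1.1 keeps out of the database, or for the 48-hour wording.

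**Conclusion.** The concern holds in a narrow form. The 2a item is scheduled once, is completed by an unblinded team and is not linked to other records. Non-serious seizures below grade 3 within 48 hours, and later ones not judged serious, reach the database as events only through that item. Infants without a 2-year visit have no 2a assessment: about 10 of 100 on the protocol's allowance, more only if deaths come on top. The 48-hour item, read literally, leaves out control infants. That asymmetry is confined to grade 3 or higher seizures not judged serious, since serious ones are SAEs in both arms.

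The documents do not show how many seizures fall into these gaps. That the missing infants are more likely to have had seizures is plausible but not stated, so neither the size nor the direction of any bias can be given. This is a cheap improvement to data collection, not a flaw that undermines the safety comparison in 4a.

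**What to change.** Make three changes:

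1. Add one CRF item, *any seizure since last contact, with date of first*, to the contacts that already include adverse event review: 24-48 h, term equivalent, VP shunt insertion, 3-6 months, 1 year, 18 months and unscheduled. Keep the 2-year item as the last in the series and update Table 1.
2. Define 2a as any seizure recorded at any contact, or in SAE, notifiable-event or anti-epileptic records, up to 2 years. State that infants who die or leave early are counted up to that point.
3. Reword the 48-hour seizure item in 6.2 to refer to the trial procedure, so that capture is the same in both arms.

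The cost is about a minute of site time per contact, a minor CRF change and a few sentences of protocol text. No new visit is needed.
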